## 5.2 Interim Analysis

No formal statistical interim analyses are planned, however data will be monitored by the Safety Monitoring Committee (SMC), in an on-going manner, to assess patient safety.

## 5.3 Disposition of Subjects

The number of patients receiving study treatment in each analysis population and the reasons for any discontinuation from the study will be presented.

## 5.4 Baseline and Demographic Characteristics

All baseline and demographic characteristics will be summarised. This will include age, age group, sex, height, weight, and Eastern Cooperative Oncology Group (ECOG) performance status at screening. Cancer history (time since initial diagnosis, type of cancer), medical history by system organ class and preferred term, and prior cancer therapies (chemotherapy, hormonal therapy, immunotherapy, monoclonal therapy, radiotherapy, other therapy) will also be summarized.

The following parameters may be used for defining and comparing the various subtypes of AML patients:

- Age Groups are defined as: <75 years and  $\geq 75$  years of age.
- AML Disease status: Relapsed and Refractory.
- AML Disease Type: Primary and Secondary
- AML Disease Cytogenetic profile: Favorable, Intermediate, Adverse and Not Done

Medical history will be coded according to Medical Dictionary for Regulatory Activities (MdDRA) version 17.0 or higher.

## 5.5 Concomitant Medication

Medications taken on or after date of informed consent are collected. Prior medications are those that started and stopped before exposure to study medication; concomitant medications are all medications taken during the study period, including those started before but ongoing at first dose.

Incidence of concomitant medication will be presented by therapeutic area and preferred drug name. Prior medications will be listed only.

Where a medication start date is partially or fully missing, and it is unclear as to whether the medication is prior or concomitant, it will be assumed that it is concomitant. Medications will be coded using WHO Drug Dictionary, Mar 2014 or higher.

## 5.6 Exposure and Compliance

BGB324 exposure will be summarized by the number of cycles started on BGB324 and duration of administration by dose cohort. Duration of BGB324 administration will be defined in days as:

(Date of Last Drug Administration – Date of First Drug Administration + 1 day).

Duration of BGB324 administration will also be summarized in weeks and defined as:

Duration of administration (in days) / 7

Total treatment exposure to BGB324 will also be characterized by total cumulative dose over the whole study and summarized by dose cohort.

For subjects in part B2, total administrations of cytarabine will be summarized by the number of cycles started, the total number of infusions (total number of days cytarabine has been administered), and total cumulative dose administered over the study. The same analysis will be performed for decitabine (part B3).

Study drug percent compliance for BGB324 will be calculated as:

$$((\text{Actual Duration}) / \text{Expected number of doses}) * 100$$

Actual Duration is the sum of each treatment duration by cycle when Dose is not missing or null.

Expected Number of Doses is defined as duration of study drug administration in days (number of cycles received \* 21 days).

Overall percent compliance will be summarized by frequency count and percentage of subjects with compliance <80%, 80 to 100%, and > 120%. Overall percent compliance will also be summarized as a continuous variable using descriptive statistics.

Number and percentage of dose reductions per cycle and overall will also be tabulated for part A and Part B.

Number and percentage of dose interruptions per cycle and overall will also be tabulated for part A and Part B. Duration of dose interruptions will also be summarised.

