11.3. Treatment Period

The following sections outline the assessments to be conducted in each part of the study. For Cycle 2 and beyond a visit window of +/-48 hours is allowed for the Day 1 visit and +/-24 hours for other visits, per protocol. For details of allowable windows around specific PK/PD sampling time-points please refer to the relevant footnotes for Tables 4-6. The timing of the Cycle 1 Day 1 and Day 4 post-dose ECGs should approximate to the PK sampling time-points. Details of allowable windows around visits and specific procedures will be included in the eCRF completion guidance documentation.

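### SAP 5.6: the compliance categories leave out >100% to 120%, and the expected-dose denominator is defined in two ways that disagree when a patient stops mid-cycle

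*SAP*

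**What the plan says.** Everything needed is in SAP 5.6, apart from the visit window.

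- **Numerator.** "Actual Duration is the sum of each treatment duration by cycle when Dose is not missing or null".
- **Denominator.** "Expected Number of Doses is defined as duration of study drug administration in days", followed in parentheses by "number of cycles received" multiplied by 21 days.
- **Duration, earlier in the same section.** "Duration of BGB324 administration will be defined in days as" last administration date minus first administration date plus one day.
- **Cycle count used for exposure.** "number of cycles started on BGB324". The compliance formula speaks of cycles received, and the SAP does not say whether that means started or completed.
- **Bands.** Overall compliance is tabulated as "compliance <80%, 80 to 100%, and > 120" per cent.
- **Continuous summary.** "Overall percent compliance will also be summarized as a continuous variable using descriptive statistics".

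The tables concerned are 14.1.9.1.1 (Part A) and 14.1.9.1.2 (Part B), both on the Safety Population. On timing, Protocol 11.3 states: "For Cycle 2 and beyond a visit window of +/-48 hours is allowed for the Day 1 visit". Cycle 1 Day 1 has no window in Tables 4 to 6 of the protocol.

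**The concern.** There are two separate defects.

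First, the bands do not cover the range. Because there is a band above 120%, the SAP expects values over 100%, so the missing interval is an omission and not a cap at 100%. A patient in that interval appears in the column total but in no row. Part B cohorts have up to 14 evaluable patients, or 20 in B5. In columns of that size, one such patient is 1/14 = 7.1% or 1/20 = 5.0%.

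Second, the denominator sentence treats two different quantities as equal. They differ whenever a patient stops before the end of a cycle, and the undefined cycle count makes even the direction of the error depend on the reading. Two programmers working from this text could produce materially different tables. Under one reading, the lowest band would mix patients who missed doses with patients who took every dose and then stopped for progression, toxicity or death.

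**Working it through.** The documents give no compliance result, so there is no planned figure to reproduce. The check applies the SAP formula, compliance = 100 × days dosed / expected doses, to simple cases.

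**Step 1: can the missing band be reached?** Inputs: daily dosing, 21-day nominal cycles, and a Day 1 window of ±2 days from Cycle 2. Assume every dose is taken, dosing continues to the visit, and the patient stops there before that day's dose.

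- Cycle 2 Day 1 one day late: 22/21 = 104.8%.
- Cycle 2 Day 1 two days late: 23/21 = 109.5%.
- Cycle 3 Day 1 two days late: 44/42 = 104.8%.
- Cycle 4 Day 1 two days late: 65/63 = 103.2%.

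None of these has a row. The largest overall value that the visit windows can produce is 109.5%.

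**Step 2: cycles received read as cycles started.** A patient takes every dose and stops on day d of cycle k:

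compliance = 100 × [21(k − 1) + d] / (21k), which is below 80% when d < 21 − 4.2k.

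| Cycle of stop | Bound on d | Stop days giving <80% | Compliance, stop on Day 10 |
|---|---|---|---|
| 1 | 16.8 | 1–16 | 10/21 = 47.6% |
| 2 | 12.6 | 1–12 | 31/42 = 73.8% |
| 3 | 8.4 | 1–8 | 52/63 = 82.5% |
| 4 | 4.2 | 1–4 | 73/84 = 86.9% |
| 5 | 0 | none | 94/105 = 89.5% |

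A mid-cycle stop always lowers the percentage, but it puts the patient below 80% only for an early enough stop in Cycles 1 to 4.

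**Step 3: cycles received read as completed cycles.** The denominator is now 21(k − 1). A Day 10 stop gives:

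- Cycle 1: denominator 0, undefined.
- Cycle 2: 31/21 = 147.6%.
- Cycle 3: 52/42 = 123.8%.
- Cycle 4: 73/63 = 115.9%, in the missing band.
- Cycle 5: 94/84 = 111.9%, in the missing band.

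**Step 4: the section's own duration as denominator.** The same patients all score 100%; for a stop on Day 10 of Cycle 1, 10/10. Missed doses still show: 28 days dosed over a 31-day span gives 28/31 = 90.3%, against 28/42 = 66.7% under cycles started × 21.

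**Step 5: interruptions.** Protocol 12.2.1 allows a toxicity interruption of up to 14 days. Under cycles × 21, a 14-day interruption over n cycles gives (21n − 14)/(21n): 33.3%, 66.7%, 77.8% and 83.3% for n = 1 to 4. Using last minus first plus 1 does not remove this when dosing resumes, because the interrupted days lie inside the span. Interruptions therefore need their own display, which SAP 5.6 already plans.

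**The case against.** The strongest reply is that this is a small descriptive table with good backup. The continuous summary keeps every value, so nobody in the missing band is lost from the report. Exposure, by-cycle administration and accountability are listed (Listings 16.2.5.1, 16.2.5.4 and 16.2.5.6), and dose reductions and interruptions are tabulated separately. All of that stands, and it limits the consequence to the categorical rows for the band gap. It does not rescue the denominator, which feeds the continuous summary as well.

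It can also be said that a visit window moves a visit and need not lengthen a recorded cycle. The protocol describes continuous 21-day cycles and leaves details of windows to eCRF guidance that is not available here. This is fair, and Step 1 is therefore conditional on dosing days up to a late visit being recorded in the cycle that is ending.

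Three stronger readings are tempting and are not supported:

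- **That a 25-day cycle gives a patient 25/21 = 119%.** With windows around the nominal schedule, a 25-day cycle needs one Day 1 visit two days early and the next two days late. Cycles of 19 and 25 days give 44/42 = 104.8% overall, and the SAP bands overall compliance. If windows run from the previous visit, no cycle exceeds 23 days.
- **That anyone who stops mid-cycle is labelled non-compliant.** The SAP has a band below 80% and no such label. Only the early stops in Step 2 fall in it, and only under the cycles-started reading.
- **That the tolerability objective rests on this table.** The safety and tolerability assessments in Protocol 8.2.1 and SAP 3.1 are adverse events, physical examination, vital signs, ECG, echocardiogram and laboratory findings. Compliance is not among them.

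**Conclusion.** Both defects are real and minor. The missing band follows directly from the text, and values of 103% to 109.5% can fall in it if dosing runs to a late Day 1 visit. The denominator is inconsistent whatever the data look like. For one patient who takes every dose and stops on Day 10 of Cycle 2, it yields 73.8%, 147.6% or 100% depending on which definition is programmed.

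The band gap affects only the categorical rows of the two compliance tables. The denominator affects the categorical and continuous compliance summaries. Neither reaches the objective response rate test, the sample size or the time-to-event endpoints. How many patients would be misplaced cannot be judged from the documents, because it depends on how many stop mid-cycle in Cycles 1 to 4 and on how cycle dates are recorded.

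**What to change.** In SAP 5.6:

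- Define expected doses once, as the section's own duration of administration (last dose date − first dose date + 1), and delete the cycles × 21 expression. The undefined cycle count then drops out of the formula.
- Make the bands exhaustive: either <80%, 80–100%, >100–120% and >120%, or <80%, 80–120% and >120%. With the new denominator, values above 100% should be rare and would mostly signal a data query, but the rows should still account for every patient.
- Add a table note that days after the last dose are not counted, so this measure describes dosing while on treatment. Keep discontinuations, interruptions and interruption duration in their separate displays.

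The cost is a few lines of SAP text, the matching table shells and a small programming change. No new data are needed.

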## 5.7 Efficacy Analysis

The endpoints to be analysed in the efficacy analysis are:

**Objective response rate [ORR]** : Proportion of patients with a best objective response such as, CR (Complete Remission), Cri (Complete Remission with Incomplete hematologic Recovery), CRp (Complete Remission with Incomplete Platelet Recovery), CRh and PR(Partial Remission) for AML patients and CR, PR, MR(Marrow Response), PMR(Partial Marrow Response) for MDS patients;

CRh is defined as, CR (<5% myeloblasts and 0% blasts in the peripheral blood) with partial hematologic recovery, defined as meeting CR criteria but with ANC > 0.5 10^9/L and platelets > 50 10^9/L responses for patients with AML.

Best Objective Response (BOR) = Best response obtain during the study participation for a patient;

**Disease control Rate (Objective Response + SD) [DCR]**: Proportion of patients with a best objective response such as, CR, CRi, CRp, CRh and PR for AML patients and CR, PR, MR, PMR for MDS patients, + SD (stable disease) as an estimate of clinical benefit;

The ORR will be summarized by;

- Age group (<75 years, >= 75);
- AML Disease Cytogenetic Profile (Favourable, Intermediate, Adverse and not done);

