16.9. Sample Size Considerations

Part A of the study follows a conventional algorithm (3+3 patients per dose level) to identify the MTD, escalating on 0/3 or 1/6 patients experiencing a DLT. Under this design, there is a 71% chance of escalation if the true but unknown rate of DLT is 20%, and <50% chance of escalation if the true but unknown rate of DLT is >30%. The operating characteristics of this 3+3 design are outlined in Table 16.

Table 16: Operating Characteristics of the 3+3 Study Design

True but Unknown Rate of DLT (%)	Probability of Escalation (%)
20	71
30	49
40	31
50	17
60	8

The total sample size of Part A depends upon whether DLT(s) is experienced at a given dose level (i.e. whether 3 or 6 patients have been treated) and how many dose levels are tested in order to reach the MTD. A minimum of 6- 10 patients will be treated at the MTD.

The sample size of up to 14 evaluable patients for Parts B1, B2, B3 and B4 and up to 20 evaluable patients in Part B5 in this study has been calculated on the basis of the following assumptions for a one-sided, within-group test of proportions, comparing an anticipated ORR of $\geq 20\%$ against the null hypothesis rate of 5%, with power 80% for a test of size 0.2. This calculation is based on statistical significance at the 0.2 level, since this will be taken as evidence of a trend worthy of further study. Although this is offered as a formal sample size calculation, it is acknowledged that for this early-stage study the analyses will be exploratory in nature, and that no account has been taken of multiplicity inherent in the assessment of several, presumably non-independent criteria, for ORR.

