Appendix 4: CYP3A4 Substrates

Examples of CYP3A4 substrates are provided below. For most up-to-date information on CYP3A4 substrates, please check the Drug Interactions Flockhart Table™ <https://drug-interactions.medicine.iu.edu/Main-Table.aspx>.

University of Indiana CYP3A4, 5, 7 P450 Drug Interactions Abbreviated "Clinically Relevant" Table of Substrates

Macrolide antibiotics:	HIV Antivirals:	HMG CoA Reductase Inhibitors:
clarithromycin	indinavir	atorvastatin
erythromycin (not 3A5)	ritonavir	lovastatin
NOT azithromycin	saquinavir	NOT pravastatin
telithromycin	nevirapine	NOT rosuvastatin
		simvastatin
Anti-arrhythmics:	Prokinetics:	
quinidine→3-OH	cisapride	Others:
		alfentanyl
Benzodiazepines:	Antihistamines:	aripiprazole
alprazolam	astemizole	boceprevir
diazepam→3OH	chlorpheniramine	buspirone
midazolam	terfenadine	carbamazepine
triazolam	Calcium Channel Blockers:	gleevec
	amlodipine	haloperidol
Immune Modulators:	diltiazem	pimozide
cyclosporine	felodipine	quinine
tacrolimus (FK506)	nifedipine	tamoxifen
sirolimus	nisoldipine	telaprevir
	nitrendipine	trazodone
PDE-5 Inhibitors:	verapamil	vincristine
sildenafil		diergotamine & ergotamine
tadalafil		fentanyl
ildenafil		

Flockhart DA. Drug Interactions: Cytochrome P450 Drug Interaction Table. Indiana University School of Medicine (2007). "/clinpharm/ddis/clinical-table/" Accessed 20 October 2016.

Appendix 5: Modified International Working Group Response Criteria in Acute Myeloid Leukemia (Cheson, 2003, Döhner, 2017)

IWG Response Criteria in AML		Bone Marrow Blasts/Myeloblast	Circulating or Peripheral Blood Blasts ^a	Absolute Neutrophil Count	Platelet Count	EMD
Morphologic Complete Remission	CR	<5% and no myeloblasts with Auer rods	None	$\geq 1.0 \times 10^9/L$ or $\geq 1,000/\mu L$	$\geq 100 \times 10^9/L$ or $\geq 100,000/\mu L$	None
CR with Incomplete Blood Count Recovery	CRi	<5% and no myeloblasts with Auer rods	None	$<1.0 \times 10^9/L$ or $<1,000/\mu L$	$<100 \times 10^9/L$ or $<100,000/\mu L$	None
Morphologic leukemia-free state	MLFS	<5% and no myeloblasts with Auer rods ^b	No hematologic recovery required			None
Partial Remission	PR	Decrease of myeloblasts % to 5% to 25% and decrease of pretreatment myeloblast % by at least 50%	All hematologic criteria of CR			
Unchanged	UN	Absence of CR, CRi or PR and criteria for PD not met				

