### 3.2 Efficacy endpoints

In AML, efficacy endpoints will be measured using objective response criteria, in evaluable patients.

- Objective Response (OR) or Stable Disease (SD) according to the revised recommendations of the International Working Group (IWG) in AML [Cheson, BGBC003 v8.0 (NO); 04 August 2020 CONFIDENTIAL Page 37 of 113 2003 and Döhner, 2017] (see Appendix 5 of the protocol). SD is defined as having unchanged disease for at least 3 treatment cycles.
- Proportion of patients with an OR + SD as an estimate of clinical benefit.
- Relapse Free Survival
- Event Free Survival
- Overall Survival
- To explore the correlation between baseline biomarker levels and clinical endpoints

In MDS, efficacy endpoints will be measured using the following response criteria.

- OR or SD according to the revised recommendations of the IWG in MDS (see Appendix 6 of the protocol). SD is defined as failure to achieve at least PR but not evidence of PD for at least 3 treatment cycles.
- Proportion of patients with an OR + SD as an estimate of clinical benefit.
- Relapse Free Survival
- Event Free Survival
- Overall Survival
- To explore the correlation between baseline biomarker levels and clinical endpoints

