**Table 1: Operating Characteristics of the 3+3 Study Design**

True but Unknown Rate of DLT (%)	Probability of Escalation (%)
20	71
30	49
40	31
50	17
60	8

The total sample size of Part A depends upon whether DLT(s) is experienced at a given dose level (i.e. whether 3 or 6 patients have been treated) and how many dose levels are tested in order to reach the MTD. A minimum of 6-10 patients will be treated at the MTD.

The sample size of up to 14 evaluable patients for Parts B1, B2, B3 and B4 and up to 20 evaluable patients in Part B5 in this study has been calculated on the basis of the following assumptions for a one-sided, within-group test of proportions, comparing an anticipated ORR of >20% against the null hypothesis rate of 5%, with power 80% for a test of size 0.2. This

calculation is based on statistical significance at the 0.2 level, since this will be taken as evidence of a trend worthy of further study. Although this is offered as a formal sample size calculation, it is acknowledged that for this early-stage study the analyses will be exploratory in nature, and that no account has been taken of multiplicity inherent in the assessment of several, presumably non-independent criteria, for ORR.

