## 5.14 Changes in Conduct or Planned Analyses from the Protocol

Following are the changes in analyses from those defined in the protocol:

- Population of analysis is updated to match with the usual definition in clinical trials. In the protocol, safety population and efficacy population have the same definition and per protocol population definition is the typically definition of efficacy population. Then, the efficacy population is updated with definition of per protocol and it is decided that no per protocol analysis will be handled.
- The exploratory objective "To explore the correlation between baseline biomarker levels and clinical endpoints". Biomarker data will be analyzed in exploratory analyses not in scope of this SAP so this analysis will be presented within biomarker analysis.

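### SAP 5.7 counts an undefined MDS category (PMR) as a response and uses a different responder list for RFS; one PMR can decide the Part B4 test

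*SAP*

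**What the plan says.** Protocol 8.2.2 and SAP 3.2 both define objective response and stable disease by the IWG criteria in Appendices 5 and 6. Appendix 5 (AML) has rows for CR, CRi ("CR with Incomplete Blood Count Recovery"), MLFS, PR, Unchanged and PD. Appendix 6 Category A (MDS) has CR, PR, Marrow CR, SD and PD, plus relapse and transformation. For AML, "SD is defined as having unchanged disease for at least 3 treatment cycles". For MDS, SD means falling short of PR without progression over at least 3 cycles.

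SAP 5.7 counts CR, CRi, CRp, CRh and PR as AML responses. For MDS it counts CR, PR, MR and "PMR(Partial Marrow Response) for MDS patients". Of the four added labels, only CRh has criteria. The list is introduced as a set of examples, so it is not closed.

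The RFS text in SAP 5.7 first admits CR/CRi/CRp/PR for AML and CR/PR/MR/PMR for MDS. Its next sentence excludes everyone who does not reach CR/CRi/CRp/PR. SAP appendix 6.7.1 ties RFS to CR alone.

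SAP 5.14 opens with "Following are the changes in analyses from those defined in the protocol" and lists two items, the analysis populations and the biomarker correlation. The response definition is not among them.

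**The concern.** ORR carries the trial's only formal tests. Protocol 16.5.2 tests each cohort one-sided against a 5% response rate and takes P<0.2 as sufficient to justify further study. That reading depends on what counts as a response. PMR would turn some MDS patients whom Appendix 6 places at stable disease into responders, by criteria that nobody has written down, in an open-label study with investigator-assessed response. The null rate stays at 5%.

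The RFS mismatch is a separate fault. Some patients who count as responders in the ORR table would be missing from the RFS table, and two programmers could read the MDS rule differently.

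**Working it through.** **1. The plan's own figure.** The inputs are "against the null hypothesis rate of 5%, with power 80% for a test of size 0.2" (Protocol 16.9), an anticipated ORR of 20%, and 14 evaluable patients in each of B1 to B4. With an exact binomial, P(X≥2) = 1 − (1−p)^14 − 14p(1−p)^13.

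- p = 0.05: 1 − 0.4877 − 0.3593 = 0.153
- p = 0.20: 1 − 0.0440 − 0.1539 = 0.802

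So 14 patients with a pass at 2 or more responders gives 80% power at an actual size of 15.3%. Thirteen patients give 76.6%. The stated sample size reproduces.

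**2. How far one patient moves the result (n = 14, null 5%).**

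| Responders | One-sided P | P<0.2? |
|---|---|---|
| 1 | 1 − 0.95^14 = 0.512 | no |
| 2 | 0.153 | yes |

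If the true rate is 5%, a cohort has exactly one responder with probability 14 × 0.05 × 0.95^13 = 0.359. In such a cohort one additional patient labelled PMR changes the conclusion.

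**3. MDS categories side by side.**

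| SAP 5.7 | Appendix 6 | Status |
|---|---|---|
| CR, PR | CR, PR | match |
| MR | Marrow CR is the nearest | no mapping given |
| PMR | none; below PR without PD for at least 3 cycles is SD | no criteria in either document |

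**4. Sensitivity for B4.** The documents give no PMR rate, so the increments are assumptions. Adding 3 or 5 percentage points to a true 5% rate:

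- p = 0.05: P(X≥2) = 0.153
- p = 0.08: P(X≥2) = 0.310
- p = 0.10: P(X≥2) = 0.415

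**5. AML categories.** SAP 5.7 defines CRh by ANC above 0.5 and platelets above 50 (×10^9/L). A CRh patient who is not in CR must have ANC below 1.0 or platelets below 100. If the Appendix 5 limits for CRi are joined by *or*, that patient is already CRi, so CRh adds no responders. The same holds for CRp, going by its name. If the limits are joined by *and*, a patient with one lineage recovered is neither CR nor CRi, and CRh or CRp would pick that patient up.

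**6. RFS against ORR, both in SAP 5.7.**

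| Best response | In ORR | In RFS, first sentence | In RFS, second sentence |
|---|---|---|---|
| AML CRh | yes | no | no |
| MDS MR or PMR | yes | yes | no |

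**The case against.** Neither the protocol nor SAP 3.2 lists which appendix categories make up objective response, so there is no fixed protocol list that the SAP demonstrably widened. Protocol 16.9 already speaks of several criteria for ORR, and efficacy is declared exploratory. MR is probably Marrow CR under another name. CRp and CRh largely overlap CRi. Investigators grade by the appendices, which contain no PMR, so the category may never be used, and individual response data will be listed so that readers can recount. The SAP also analyses four country protocols (Germany v10.0, Norway v8.0, US v9.0, Italy v4.0). Only US v10.0 was available, so another version might define PMR.

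Much of this stands and limits the point. It does not rescue PMR. SAP 3.2 itself refers to Appendix 6 for MDS response, and neither document defines the category that SAP 5.7 then counts. The absence of a list in the protocol makes a closed list in the SAP more necessary. Nor does it touch the RFS rule, which conflicts with text in the same SAP section.

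Including Marrow CR is itself a choice: read literally, the Appendix 6 definition of SD could also take in a Marrow CR that falls short of PR. Appendix 6 does give Marrow CR its own row and criteria, which PMR lacks.

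**Conclusion.** The point holds for Part B4 and for the RFS rule. In B4 one PMR can reverse the P<0.2 conclusion. The rise from 15.3% to 31.0% or 41.5% rests on three assumptions: 14 evaluable patients, a true rate of 5% without PMR, and 3 or 5 added points. The statement that 5.14 declares no change is checked against US v10.0 only.

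A reader might infer more than the documents support:

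- **That the false-positive rate is inflated in every cohort.** The AML cohorts are little affected if CRp and CRh are subsets of CRi.
- **That MLFS is shut out of disease control.** The SAP does not name it. Appendix 5 defines Unchanged without mentioning MLFS, so an MLFS patient could fall there and count as SD if sustained. Its place is unsettled, and leaving it out of ORR would be conservative.
- **That Appendix 5 leaves a gap between CR and CRi.** The two count limits sit in separate table cells with no visible connector. That may be an effect of text extraction, and it is in any case a protocol question.
- **That PMR will be filled in after the results are known.** The plan leaves room for this, but nothing in it says so.

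**What to change.** Before database lock, amend the SAP as follows.

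- In 5.7, give a closed responder list in appendix terms for the tested ORR. AML: CR, CRi (with CRp and CRh shown as subsets) and PR. MDS: CR, PR and Marrow CR, with MR mapped to Marrow CR.
- Take PMR out of the tested ORR and show it on a separate line with a written definition.
- Use the same list for RFS and remove the conflict between its two sentences.
- Report MLFS on its own line and state whether it counts in DCR.
- Record these changes in 5.14, after checking the four country protocol versions that the SAP cites.

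Separately, as a protocol clarification, confirm whether the CRi count limits in Appendix 5 are joined by *or*.

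The SAP changes cost wording and programming, with no new data. The downside is that the B4 ORR may be slightly lower. If Appendix 5 itself needs correcting, that is a protocol matter and may touch several country versions.
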